Continuous pulse oximetry (SpO₂) monitoring has revolutionized detection of oxygen desaturation in operating rooms and other high-risk areas, improving outcomes in those settings.^{1,2} However, research suggests that overuse of continuous SpO₂ monitoring in stable children with bronchiolitis who are unlikely to benefit from it is low-value care that places some children at risk of adverse outcomes.³⁻¹² Despite national guidelines^{13,14} discouraging continuous pulse oximetry use in stable bronchiolitis patients, 46% of those infants and children are continuously monitored.

Objectives:

The primary objective is to measure the feasibility, acceptability, and appropriateness of audit and feedback with educational outreach as a strategy to align continuous pulse oximetry use in stable bronchiolitis patients with evidence and guideline recommendations.

Study Design:

Pragmatic, prospective, non-randomized, single-arm feasibility pilot implementation with the intervention delivered at the hospital unit level.

Setting/Participants:

The pilot will be performed on non-ICU hospital units that care for bronchiolitis patients at up to 10 total hospitals in the United States. The primary subjects are hospital staff who order or manage continuous pulse oximetry monitoring for bronchiolitis patients. Secondary subjects are patients age 2 through 23 months with a primary diagnosis of bronchiolitis.

Study Interventions and Measures:

The intervention is an audit and feedback strategy that includes providing the hospital's own continuous pulse oximetry use data back to them on a weekly basis. The data will be accompanied by staff-targeted educational materials and outreach sessions summarizing the current evidence and guideline recommendations for continuous pulse oximetry use in bronchiolitis.

Primary measurements include measures of feasibility, acceptability, and appropriateness of the audit and feedback strategy. Secondarily, we will analyze continuous pulse oximetry use rates and validate an alternative semi-automated data collection strategy.

1 BACKGROUND INFORMATION AND RATIONALE

1.1 Introduction

Continuous pulse oximetry (SpO₂) monitoring has revolutionized detection of oxygen desaturation in operating rooms and other high-risk areas, improving outcomes in those settings.^{1,2} However, research suggests that overuse of continuous SpO₂ monitoring in stable children with bronchiolitis who are unlikely to benefit from it is low-value care that places some children at risk of adverse outcomes.³⁻¹²

Despite national guidelines^{13,14} discouraging continuous pulse oximetry use in stable bronchiolitis patients, 46% of those infants and children are continuously monitored (not yet published data from a multicenter study performed in 56 hospitals led by investigators on this proposal).

This study aims to pilot an audit and feedback strategy to align continuous pulse oximetry use in stable bronchiolitis patients with evidence and guideline recommendations in preparation for a multicenter cluster-randomized hybrid trial.

1.2 Relevant Literature and Data

1.2.1 Bronchiolitis SpO₂ monitoring guidelines

Appropriate use of SpO₂ monitoring in children with bronchiolitis is guided by the American Academy of Pediatrics (AAP) Clinical Practice Guideline for the Diagnosis, Management, and Prevention of Bronchiolitis¹³ and Society of Hospital Medicine Choosing Wisely recommendations.¹⁴ The AAP Guideline was published by [name] (Advisory Committee member) and colleagues in 2014.¹³ The Guideline states that "*Clinicians may choose not to use continuous pulse oximetry for children with a diagnosis of bronchiolitis*," citing intermittent monitoring benefits including shorter length of stay, decreased alarm fatigue, and decreased cost. The Society of Hospital Medicine Choosing Wisely in Pediatric Hospital Medicine workgroup took a stronger stance against monitoring, stating "*Do not use continuous pulse oximetry routinely in children with acute respiratory illness unless they are on supplemental oxygen.*"¹⁴

1.2.2 Research published since bronchiolitis SpO₂ monitoring guidelines

Since publication of the AAP Guideline and Choosing Wisely recommendations, 3 randomized trials,³⁻⁵ 2 nonrandomized studies,^{6,7} and 1 expert commentary¹⁵ have further strengthened the evidence base against using continuous SpO₂ monitoring in favor of intermittent SpO₂ measurement in children with bronchiolitis not requiring supplemental oxygen. The research below demonstrates that intermittent SpO₂ monitoring is a safe alternative,^{3,7} those who are continuously monitored unnecessarily are at risk of adverse outcomes including prolonged length of stay,^{5,8,9} iatrogenic harm,¹⁰ and increased costs,⁵ and false SpO₂ monitor alarms contribute to alarm fatigue.^{11,12} McCulloh et al performed a randomized trial comparing continuous versus intermittent SpO₂ monitoring among children with bronchiolitis at 4 hospitals who had stable oxygen saturations of 90% or higher off supplemental oxygen.³ They found that patients who underwent intermittent SpO₂ measurement did not have increased urgent care escalation or respiratory interventions, confirming its safety.

Schuh et al performed a randomized trial among infants presenting to an emergency department with bronchiolitis.⁴ Infants were randomized to have their SpO₂ measured either with an oximeter with true SpO₂ displayed or a modified oximeter with falsely elevated SpO₂ displayed (+3 percentage points). Patients whose SpO₂ was artificially elevated were less likely to be hospitalized but had no significant differences in other clinical outcomes, including no difference in subsequent unscheduled follow up visits for bronchiolitis. We interpret these findings as indicating that continuous pulse oximetry likely identifies minor desaturations that do not impact outcomes but are over weighted in clinical decision making (in this study, the decision to admit).

In the Bronchiolitis of Infancy Discharge Study (BIDS), a randomized controlled trial of hospitalized infants with bronchiolitis, Cunningham et al randomized infants to be continuously monitored using either a standard pulse oximeter or a modified oximeter that falsely inflated SpO₂, displaying a measured value of 90% as 94%.⁵ They found that supplemental oxygen was provided less often and

for shorter periods of time in the group with SpO₂ values falsely inflated, an expected outcome. However, they also found that infants were discharged 10 hours sooner in the group with SpO₂ values falsely inflated, and yet there were no differences in any adverse effects of the falsely inflated oxygen saturation value, including readmission or time until return to daycare. In an economic analysis of BIDS, the standard oximeter group had significantly greater hospital costs than the modified group, primarily driven by costs of the hospital bed, supplemental oxygen, and oximeter probes.¹⁶ Like Schuh's study, we interpret these findings as indicating that continuous pulse oximetry likely identifies minor desaturations that do not impact patient outcomes but are over weighted in clinical decision making, unnecessarily prolonging oxygen administration and length of hospital stay and increasing costs.

Principi et al performed a cohort study of infants presenting to an emergency department with bronchiolitis who were well enough to be discharged home.⁶ Prior to discharge, researchers applied pulse oximeters to the infants. The oximeters had alarms disabled and their displays did not show SpO₂ values. They collected the oximeters 72 hours later. They found that half of these infants deemed well enough for discharge had desaturations to 80% or less for at least 1 minute and one-quarter had desaturation to 70% or less for at least 1 minute. There were no differences in rates of return medical visits or subsequent hospitalizations between infants who experienced desaturations and those who did not. We interpret these findings as indicating that brief desaturations to levels that would likely have been treated if they occurred in hospital are common in patients with bronchiolitis at home, but are not associated with adverse outcomes.

Schondelmeyer et al evaluated a quality improvement intervention targeting reduction of continuous pulse oximetry in children with bronchiolitis and asthma when they no longer required supplemental oxygen.⁷ Their intervention included staff education, checklists, and electronic health record clinical decision support. They found a reduction of median time on continuous pulse oximetry from 10.7 to 3.1 hours without a difference in rapid response team activations, ICU transfers, or readmissions. This study confirms the safety of the AAP Guideline and Choosing Wisely recommendations, and supports the practice of removing continuous pulse oximetry after supplemental oxygen is discontinued and replacing it with intermittent SpO₂ monitoring.

In a 2017 BMJ expert commentary, "When technology creates uncertainty: pulse oximetry and overdiagnosis of hypoxaemia in bronchiolitis,"¹⁵ Quinonez et al reviewed the literature above and argue that the widespread use of pulse oximetry in stable bronchiolitis patients leads to overdiagnosis of hypoxemia. Overdiagnosis is when a true abnormality is discovered, but awareness of the abnormality does not benefit the patient.¹⁷ The authors conclude that "current body of evidence suggests that we should challenge assumptions regarding the detection and aggressive management of borderline hypoxemia in non-critically ill infants with bronchiolitis," because current overuse of continuous pulse oximetry has led to overdiagnosis of clinically insignificant hypoxemia that contributes to unnecessary resource utilization and risk of patient harm.

1.2.3 Unpublished trials of continuous versus intermittent SpO₂ monitoring in bronchiolitis

We identified 2 randomized controlled trials of continuous versus intermittent SpO₂ monitoring in bronchiolitis led by [name] in Toronto. The first trial is a single center pilot that has been completed.¹⁸ The second is a 6-center trial that is ongoing.¹⁹ While results of the intervention on the primary outcome (length of stay) are not yet available, in a personal communication the Principal Investigator reported that among the 89 patients randomized to intermittent (as opposed to continuous) SpO₂ monitoring to date, none have experienced adverse safety events attributable to the less intensive intermittent monitoring intervention.²⁰

1.2.4 Results of Best Evidence for Effective Pediatric (BEEP) Monitoring Study

The BEEP study, performed in 2018 (not yet published) and led by [name], MSc used the RAND/UCLA Appropriateness method and a panel of experts nominated by leaders of national nursing, physician, human factors, and respiratory therapy organizations as well as a family advocacy organization to develop consensus guidelines for physiologic monitoring in hospitalized children in non-ICU settings. Pertinent to this proposal, the expert panel determined the following scenarios to be appropriate and necessary:

- Children hospitalized with routine bronchiolitis and an SpO_2 value of $\geq 90\%$ without supplemental oxygen in the absence of witnessed apnea or cyanosis should NOT receive continuous pulse oximetry monitoring, instead they should receive intermittent pulse oximetry measurement
- Children weaned from supplemental oxygen should be transitioned to intermittent oximetry measurement within 1 hour if oxygen saturations are stable at $\geq 90\%$ unless otherwise indicated by diagnosis or condition.

1.2.5 Measurement of pulse oximetry use using direct observation during the 2018-19 bronchiolitis season

[figure not shown]
From December 2018 through March 2019, our team performed a 56-center observational study within the Pediatric Research in Inpatient Settings (PRIS) Network measuring pulse oximetry use in stable infants and children not requiring supplemental oxygen.²¹ This is the population for whom the AAP and Choosing Wisely support avoiding the use of continuous pulse oximetry.

The study aimed to include exclusively patients for whom continuous pulse oximetry is not indicated according the AAP and Choosing Wisely guidelines: Children 8 weeks-23 months old with primary diagnosis of bronchiolitis on most recent physician note, hospitalized on generalist services in non-ICU areas, and not currently on any supplemental oxygen or room air flow support. We excluded infants born at <28 weeks, those receiving home oxygen or positive pressure ventilation, and those with major cardiac, respiratory, neuromuscular, immunologic, and oncologic comorbidities. This project was funded by NHLBI and was approved by the CHOP IRB as the reviewing IRB (CHOP IRB# 18-015070).

In this study that included over 3600 in-person assessments of pulse oximetry monitoring status, we found that the overall monitoring rate across all hospitals was 46%, with a very wide range of variation, ranging from hospitals that monitor $<5\%$ of these patients to hospitals that monitor $>85\%$ of these patients (results not yet published; see figure below). These results support efforts to reduce continuous pulse oximetry in stable bronchiolitis patients in outlier hospitals with high use rates.

Prior to submitting a subsequent grant that will aim to de-implement continuous pulse oximetry in a well-defined stable bronchiolitis population, we must establish the feasibility of a foundational audit and feedback strategy for addressing continuous pulse oximetry overuse.

Continuous pulse oximetry overuse rates (by hospital, unadjusted, with 95% CIs)

1.2.6 Effective strategies for implementing practice guidelines

In a recent report from the American College of Cardiology/American Heart Association Task Force on Clinical Practice Guidelines, evidence from the published implementation science literature was presented describing effective strategies to enhance the adoption and implementation of clinical practice guidelines.²² The review concluded that audit and feedback and educational outreach strategies were the most effective in improving outcomes measuring processes of care as well as clinical outcomes. However, the specific aspects of audit and feedback that make this strategy effective (e.g. who the feedback data are delivered to, what information is delivered, is comparison data provided, are data presented graphically, what is the lag time between data collection and feedback, etc) are not well established, but are an active area of inquiry in the field of implementation science. The subsequent trial that we will plan based upon the results of this pilot will secondarily aim to elucidate mechanisms that contribute to the effectiveness of differing configurations of audit and feedback.

1.3 Compliance Statement

This study will be conducted in full accordance with all applicable Children's Hospital of Philadelphia Research Policies and Procedures and all applicable Federal and state laws and regulations. All episodes of noncompliance will be documented.

The investigators will perform the study in accordance with this protocol and will report unanticipated problems involving risks to subjects or others in accordance with Children's Hospital of Philadelphia IRB Policies and Procedures and all federal requirements. Collection, recording, and reporting of data will be accurate and will ensure the privacy, health, and welfare of research subjects during and after the study.

2 STUDY OBJECTIVES

2.1 Primary Objective (or Aim)

The primary objective of this study is to measure the feasibility, acceptability, and appropriateness of audit and feedback with educational outreach as a strategy to align continuous pulse oximetry use in stable bronchiolitis patients with evidence and guideline recommendations.

2.2 Secondary Objectives (or Aim)

The secondary objectives are to:

- Measure continuous pulse oximetry use rates in children with bronchiolitis who are not requiring supplemental oxygen administration.
- *In hospitals with “medical device integration”* in which data from physiologic monitors are sent directly to the electronic health records, we will:
 - Validate that the medical device integration data in the electronic health record reflects the findings of direct in-person observation described above as the gold standard.

3 INVESTIGATIONAL PLAN

3.1 General Schema of Study Design

This is a pragmatic,²³ prospective, non-randomized, single-arm feasibility pilot implementation with the audit and feedback plus educational outreach intervention delivered at the hospital unit (i.e. ward) level.

This study does not directly involve making any changes to patient care – it only involves presenting data, guidelines, and evidence to clinical staff who make independent decisions about their own actions related to pulse oximetry monitoring in bronchiolitis. Any individual clinicians who do not wish

to participate may choose not to interact with the electronic communications and may choose to not attend meetings where this intervention is discussed.

On the Pragmatic-Explanatory Continuum,²³ this study is highly pragmatic for the following reasons (see cited article for detailed explanation of domains):

- **Eligibility criteria:** The same bronchiolitis patients who would likely be a candidate for the audit and feedback intervention if it was being provided in usual care are also eligible for this intervention since it is applied at the hospital unit level.
- **Recruitment:** The audit and feedback intervention will be delivered to the same health care professionals who are involved in the decisions or actions surrounding the initiation or discontinuation of continuous pulse oximetry monitoring in usual care.
- **Setting:** The pilot is being performed in hospital settings that are identical to the types of settings where we intend the results to be applied.
- **Organization:** Given the highly pragmatic nature of this study, the intervention will be delivered into each hospital using the same structures of care used locally for making improvements in bronchiolitis care delivery.
- **Flexibility in intervention delivery:** Consistent with the idea that interventions can be tailored to local context, we will allow for flexibility/adaptation/tailoring in the content and format of the educational materials and outreach sessions. Thus, the methodology of exactly how to deliver this intervention is not rigidly prescriptive in this protocol. In addition, it is possible that some sites will be performing concurrent quality improvement interventions targeting pulse oximetry overuse. We will seek to fully understand when and how any potential quality improvement interventions interact with this study but we will not restrict sites from performing separate improvement initiatives nor will we will regulate or oversee their concurrent quality improvement projects.
- **Flexibility in adherence to the intervention:** While we will monitor health care professionals' engagement with the interventions and the resulting pulse oximetry use that results at the patient level, as in usual care, there are no special measures in place beyond what would occur in the course of a practice change in the usual care of bronchiolitis.

3.2 Allocation to Treatment Groups and Blinding

N/A: This is a single-arm study.

3.3 Study Duration, Enrollment and Number of Sites

The intervention period will last between 2-4 months depending on the timing relative to the local epidemiology-dictated bronchiolitis season.

The primary subjects are hospital staff. Secondary subjects are patients age 2 through 23 months with a primary diagnosis of bronchiolitis.

3.3.1 Duration of Study Participation

- Hospital staff: 2-4 months.
- Patients: minimum of 1 day, maximum of the duration of their entire hospitalization (maximum 4 months; anticipated average of 1-3 days).

3.3.2 Total Number of Study Sites/Total Number of Subjects Projected

The study will be conducted in up to 10 hospitals in the United States.

Primary subjects exposed to the intervention (hospital staff): Since the intervention is occurring at a unit-wide level and we are not collecting any identifiers on these primary subjects, it is not possible to accurately measure the actual number of staff whose behavior could potentially have been impacted by the intervention. It also will not be possible to identify when hospital staff are exposed to the intervention repeatedly over time. In order to best estimate this number, we will "count" the

involvement of 100 hospital staff per unit during the entire intervention period. Based on an average of 5 available units per hospital in candidate hospitals, we can estimate 10 hospitals * 5 units per hospital * 100 staff per unit = 5,000 hospital staff subjects, acknowledging that this number will not be completely accurate but is a reasonable estimate. When we report the “actual” number of primary exposed subjects involved for continuing reviews and study closure, we will report 100 * the total number of units involved in the study.

Primary subjects completing the questionnaires (hospital staff): We will aim for 100 completed questionnaires per hospital x 10 hospitals = 1,000 primary subjects completing the questionnaires. Since these 1,000 will be drawn from within the 5,000 listed above, they will not add to the overall subject total.

Secondary subjects - Patients: We project collecting data on a maximum of 300 unique bronchiolitis patients per hospital * 10 hospitals = 3,000 patients.

3.4 Study Population

3.4.1 Inclusion Criteria

3.4.1.1 Primary subjects - Hospital staff

- 1) Nurses, physicians, physician assistants, nursing assistants, or respiratory therapists
- 2) Providing care to patients on units included in the study.

3.4.1.2 Secondary subjects - Patients

- 1) Males or females 8 weeks through 23 months old hospitalized on non-ICU wards
- 2) Cared for by generalist inpatient services (e.g. general pediatrics, hospital medicine)
- 3) Primary diagnosis of acute bronchiolitis according to hospital chart
- 4) Not currently requiring supplemental oxygen therapy or nasal cannula flow at an FiO₂ of 21% (room air flow)

3.4.2 Exclusion Criteria

3.4.2.1 Primary subjects - Hospital staff

- 1) None. Staff may self-exclude by choosing not to interact with the electronic communications and may choose to not attend meetings where the intervention is discussed.

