4 STUDY PROCEDURES

4.1 Pre-intervention period

- Implementation champions identified, local teams formed
- Local team members will meet with leadership on each potential unit; unit leadership will be given the opportunity to opt their unit out of the study for any reason.
- Implementation champions & teams perform educational outreach sessions on participating units
 - describing current guidelines
 - summarizing the evidence behind the guidelines
 - discussing potential alternatives to continuous pulse oximetry monitoring for patients in whom guidelines do not advise continuous pulse oximetry
- Distribution/dissemination of educational materials (e.g. slide presentations, posters, flyers, videos) to hospital staff working on study units focused on the bullet points above
 - materials collaboratively developed by the CHOP team and local implementation teams, with site-specific tailoring by the local implementation teams

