6.3 Statistical Methods

6.3.1 Questionnaire-based methods (AIM, IAM, FIM)

We will generate average scores for each item and for each measure, stratified by hospital and role (e.g. nurse, physician).

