8.5 Recruitment Strategy

The pragmatic approach to recruitment of health care professionals and patients for the intervention has been described in previous sections.

For the data collection in-person observational rounds, site investigators will identify all patients currently admitted to their hospital's non-ICU pediatric wards with bronchiolitis by reviewing the census of each unit that cares for children with bronchiolitis and examining the charts of patients meeting age criteria to determine if they are eligible. Eligibility screening does not involve recording any data until the patient is determined to be eligible and is enrolled.

For the primary objective, measuring feasibility, acceptability, and appropriateness using the validated questionnaire instruments, site PIs will distribute the questionnaire to the following health care professional types who worked on an intervention unit in a role involving the care of patients with bronchiolitis during the intervention period:

- Attending physicians
- Resident physicians
- Nurses
- Nursing assistants
- Physician assistants
- Respiratory therapists
- Other relevant staff (e.g. if a hospital's bronchiolitis care team includes staff who educate parents about their child's condition prior to discharge, we would include them here)

Questionnaires will be distributed in paper and electronic formats. Paper questionnaires will be distributed during unit-based events such as safety huddles,^{24,25} staff meetings, and rounds and subsequently entered into a CHOP-based REDCap form by the site investigative team or scanned and emailed to the CHOP-based study email address. Electronic questionnaires will be distributed using CHOP-based REDCap survey distribution tools to track responses and nonresponses. In order to distribute, site PIs will work with unit leadership within each discipline listed above to identify potential eligible health professional subjects. Site PIs will submit a list of email addresses of these potential subjects to CHOP study leadership, who will enter these into the CHOP-based REDCap survey distribution system.

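### The plan does not separate staff who deliver the strategy from staff who receive it in the primary AIM, IAM and FIM scores, so those scores may mix the two views

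*Combined protocol and SAP*

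**What the plan says.** Staff eligibility (3.4.1.1) has two conditions: a listed profession, "Nurses, physicians, physician assistants, nursing assistants, or respiratory therapists", and "Providing care to patients on units included in the study". The exclusion entry (3.4.2.1) reads "None. Staff may self-exclude by choosing not to interact with the electronic communications". For the questionnaire itself, 8.5 says that "site PIs will distribute the questionnaire to the following health care professional types who worked on an intervention unit" in a role involving bronchiolitis care, and adds other relevant staff. Nothing there leaves out the implementation team.

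The same document describes who carries the strategy. Under 4.1, "Implementation champions & teams perform educational outreach sessions on participating units", using "materials collaboratively developed by the CHOP team and local implementation teams, with site-specific tailoring by the local implementation teams". Under 4.2, the teams run the observation rounds and the local team passes the weekly results to clinicians.

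Section 5.4.2 lists the questionnaire content: hospital, unit, profession, whether the person cared for bronchiolitis patients, demographics, AIM, IAM, FIM and supplemental items. Section 6.1 makes the scores the primary endpoints. The analysis in 6.3.1 is: "We will generate average scores for each item and for each measure, stratified by hospital and role", where the examples of role are professions.

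**The concern.** The strategy is delivered by one group and aimed at another, but the measurement does not keep that distinction. A clinician who wrote the slides, ran the sessions and presented the data would be rating his or her own work. That clinician's answer would enter the same average as those of colleagues on the receiving end.

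These scores are the main product of the pilot and are meant to inform a later cluster-randomized trial. If a favourable hospital or role average partly reflects the project team, it says less about how staff elsewhere would take to the strategy. Such a bias does not shrink as more forms come in, provided the team's share stays the same.

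**Working it through.** **1. The plan's own figure.** Inputs from 6.4: null mean 3.0, expected mean 4.0, SD 3, alpha 0.05, about 100 questionnaires per hospital for 90% power, 73 for 80%. With a two-sided one-sample t-test, the noncentrality is (4.0 − 3.0)/3 × √n.
- n = 73: noncentrality 2.85, power 0.802.
- n = 100: noncentrality 3.33, power 0.910; 90% is reached at n = 97.

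Both stated figures reproduce.

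**2. Shift in a mean.** Let p be the share of respondents who are team members and g the team mean minus the non-team mean. Then

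mean of all = (1 − p) × non-team mean + p × team mean = non-team mean + p × g,

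so the shift is p × g. The documents give neither p nor g; both are assumed and shown as a range.

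| Team members | g = 0.5 | g = 1.0 | g = 2.0 |
|---|---|---|---|
| 3 of 100 | 0.015 | 0.03 | 0.06 |
| 5 of 100 | 0.025 | 0.05 | 0.10 |
| 10 of 100 | 0.05 | 0.10 | 0.20 |
| 20 of 100 | 0.10 | 0.20 | 0.40 |
| 3 of 20 (one role) | 0.075 | 0.15 | 0.30 |
| 5 of 20 (one role) | 0.125 | 0.25 | 0.50 |

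A negative g, possible for feasibility, gives the same sizes downward.

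**3. Comparison with the planned contrast and precision.** The planned contrast is 1.0 point. The 95% half-width of a hospital mean is 1.984 × SD/√100: 0.60 at the stated SD of 3, and 0.20 if the SD were 1 (assumption). In a stratum of 20 it is about 1.40 or 0.47. For the 1,000 forms projected in 3.3.2, ignoring clustering, it is 1.96 × SD/√1000: 0.19 or 0.06. A shift of 0.10 is thus small against one hospital's uncertainty, but exceeds that of a pooled mean if the SD is near 1.

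**4. Effect on the test against neutral.** Suppose non-team staff truly average 3.0, and 10 of 100 respondents are team members with g = 1.0. The two-sided rejection rate rises from 5% to 6.3% at SD 3, or to 16.8% at SD 1.

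**5. Power after setting the team aside.** The same t-test with fewer responses gives 0.895 at n = 95, 0.879 at n = 90 and 0.838 at n = 80.

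**The case against.** Three stronger readings are tempting.

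*That deliverers certainly are among the raters.* The documents do not say who the champions are, how many there are, or whether they work clinically on study units. The exclusion entry itself concerns opting out of the intervention. Recipients are chosen under 8.5 by site PIs with unit leadership, who could leave the team off. What stands is that nothing requires them to.

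*That deliverers cannot be told apart afterwards.* This is not established. The supplemental items sit in an eIRB section outside the document (10.2) and might ask about team role. Electronic surveys go to a submitted email list, and replies are tracked. The documents do not say whether that link is kept for analysis. Separation is least certain for paper forms: they are handed out at huddles, staff meetings and rounds, which 4.2 also names as feedback settings, and no link to an invitation is described.

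*That the scores are biased upward.* This is plausible for acceptability and appropriateness, but nothing in the documents shows it. For feasibility the team bears the work of rounds at least twice a week, chart review and weekly feedback, and may score lower. Nor do the documents show that deliverers return the form more often.

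It is also fair to say that the objective in 2.1 is not confined to recipients. Deliverers' views bear directly on feasibility, so removing them from the main score is debatable. Section 6 puts little weight on power, and the plan sets no score threshold for proceeding, so no stated decision turns on a shift of 0.05 to 0.10. The upper end of the table is also hard to reach: if non-team staff average 4.0 and the scale ends at 5 (assumption), g cannot exceed 1.0, which caps the 20-of-100 case at 0.20.

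These points limit the size and certainty of the concern. They do not supply the missing distinction in the listed fields or in 6.3.1.

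**Conclusion.** The point holds in a conditional form. Team members who also give care on a study unit are not kept out of the questionnaire, no listed field identifies them, and no planned analysis sets them apart. The primary scores may therefore combine deliverers' and recipients' views in unknown proportion.

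Under the assumed ranges the shift in a hospital mean is 0.015 to 0.40 points against a planned contrast of 1.0. It is modest for a few members among 100 and larger where the team makes up much of a role stratum. What drives it is the team's share; a small stratum with no team members is unaffected. This is a cheap improvement worth making before the forms go out, and does not show that the primary endpoint is invalid.

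**What to change.** Check the supplemental items first. If they do not already ask it, add one yes/no item to 5.4.2 on whether the respondent was a champion, site investigator or local implementation-team member. That section already allows minor changes to items before administration. Put the item on the paper form as well, where the information may otherwise be lost.

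In 6.3.1, report AIM, IAM and FIM three ways: all respondents, non-team respondents, and team members. Pool the team results across hospitals where cells are small. This avoids having to settle whose view is the right primary one.

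The cost is one item and a few table rows. The non-team score loses some responses: power is about 0.90 with 95 of 100 and 0.88 with 90 of 100. Keeping 100 non-team forms would take 100/0.95, or 106, or 100/0.90, or 112. The real drawback is confidentiality. With hospital, unit, profession and demographics already recorded, and paper forms possibly entered by the site's own team, a yes answer could point to one person. Pooling limits that risk in reporting but does not remove it at data entry.
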